Health system costs: This analysis will examine intervention costs and incremental medical costs associated with the intervention. Cost data will be analyzed using the same methods described above with factors for study arm and health care system/clinic strata, using generalized Gamma regression, which include as special cases lognormal, Gamma and Weibull. The primary dependent variable will be healthcare cost, in total and separated into inpatient, outpatient, and pharmacy cost buckets. The primary independent variable will be the intervention arm the patient was randomized to. Results will be stratified by healthcare system.

Power Assessment

We first estimated sample size required to achieve 80% power for the desired change in the primary outcome, then used current data to show we will be able to achieve this sample size.

Power and sample size: Required sample size was estimated for the primary outcome PDC during the 12 months following randomization. Preliminary data from the VA were used for these estimates. We made the following assumptions: a) Significance using two-sided level 0.05 tests, b) Power at least 80%; c) Difference between treatments in PDC of 10 percentage points; d) Bonferroni adjustment for the 6 pairwise comparisons among the 4 study arms, resulting in adjusted level 0.05/6; e) Analysis stratified by health care system; and f) Within-system and within-treatment residual standard deviation of 12 month PDC equal to 0.247 (mean 0.771), obtained by analysis of 594,466 veterans during the period 01/01/2010 – 09/30/2012 who were prescribed CVD medications. The large SD is due to a highly left-skewed PDC distribution. (We base sample size estimation on t-tests rather than the proposed binomial models since we do not have estimates of quantities needed to carry out power simulations. We may be able to obtain data for the PDC outcome for a set of baseline patients, in which case we will consider a refined power analysis.) Using these assumptions and estimates, and comparing any two treatments using a linear model with the above residual standard deviation of PDC, we estimate using sample size functions in R that we will need N=154 subjects per treatment arm, total

across the three health care systems, for a total of 616 subjects to be randomized across the three health care systems.

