799

800

795

Compensation

Patients participating in interviews will be offered a gift card for an online store valued at \$50 for their participation.

801 802

803

806

804 1. Gurol-Urganci I, de Jongh T, Vodopivec-Jamsek V, Atun R, Car J, Mobile phone 805 messaging reminders for attendance at healthcare appointments (Review). Cochrane Database of Systematic Reviews. 2013(12).

- Data Science to Patient Value (D2V)
 UNIVERSITY OF COLORADO ANSCHUTZ MEDICAL CAMPUS

 de Jongh T, Gurol-Urganci I, Vodopivec-Jamsek V, Car J, Atun R. Mobile [contact] messaging for facilitating self-management of long-term illnesses (Review). Cochrane 809 Database of Systematic Reviews. 2012(12). 810 3. Vodopivec-Jamsek V, de Jongh T, Gurol-Urganci I, Atun R, Car J. Mobile phone 811 messaging for preventive health care (Review). Cochrane Database of Systematic 812 Reviews. 2012(12).
- 813 4. Head KJ, Noar SM, Iannarino NT, Harrington NG. Efficacy of text messaging-based 814 interventions for health promotion: A meta-analysis. Social Science & Medicine. 815 2013;97:41-48.

Summary of revision

5 6 7

This revision of the analytic plan was motivated by several external disruptions during the conduct of the study, and by a brief examination of treatment-blinded outcome data. The main changes to the original Statistical Analysis Plan (SAP) involve the method used to model the primary PDC outcome, detailed specification of adjustment covariates, and adjustment for differing lengths of follow-up due to death, changes in prescriptions, or external disruptions. No changes to primary or secondary outcomes are proposed. The changes of substance occur only in Sections 3.1.a-e.

EFFECTIVENESS STATISTICAL ANALYSIS PLAN (SAP) - REVISED 04/20/2023

1. Study summary

The primary outcome will be medication adherence defined as the proportion of days covered (PDC) in the 12 months post randomization. This will be a composite measure across a patient's multiple medications and will be assessed using pharmacy refill data. Secondary outcomes will include intermediate clinical measures (e.g., BP control), CV clinical events (e.g., hospitalization for myocardial infarction) and procedures (e.g. PCI), medication-associated clinical events (e.g., syncope in patient on anti-hypertensive therapy), healthcare utilization, and costs. These outcomes will also be assessed at 12 months, with cost and utilization also assessed for specific components as described below.

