Primary and secondary outcomes: The study outcomes have been selected based on input directly elicited from patients and other stakeholders. The primary outcome is adherence to CV medications as measured by 12-month composite proportion of days covered (PDC). Secondary outcomes include alternate measures of CV medication adherence, clinical events (e.g., event times for stroke, MI, mortality), utilization of care (e.g., hospitalizations or clinic visits for CV-related reasons), and costs of healthcare utilization. Subjects will be followed for at least 12 months following randomization to assess these secondary outcomes. Subjects who have more than one year of follow-up (up to 3 years depending on when they are enrolled during years 2-3) will continue to be followed for secondary outcomes.

Ascertainment of Outcomes: Data for the primary outcome PDC will be obtained using pharmacy records from each of the healthcare systems during the 365-day follow-up. The medication refill data needed to assess PDC is routinely collected in the pharmacy databases of each of the participating sites.

During the UG3 phase, the data management workgroup developed definitions and specifications for the secondary outcomes that will be captured from the EHR at each of the three healthcare systems. International Classification of Diseases, Ninth and Tenth Revision (ICD 9 and 10), CPT and DRG codes identifying CV clinical events, CV procedures, and adverse medication associated clinical events have been compiled to ensure accurate identification these outcomes. Outcome measures for BP and LDL have also been standardized using NIH Collaboratory definitions for these standardized EHR data elements (**Appendix V**). The data core successfully used EHR and administrative data to assess for each of these outcomes during the UG3 pilot year.

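### Generalized gamma regression is named for inpatient cost, where about 91% (Denver Health) and 86% (VA) of patients are projected to have exact zeros that a maximum-likelihood fit cannot include

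*Combined protocol and SAP*

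**What the plan says.** The protocol (Planned Analysis, Health system costs) analyses cost by "generalized Gamma regression, which include as special cases lognormal, Gamma and Weibull". The dependent variable is "healthcare cost, in total and separated into inpatient, outpatient, and pharmacy cost buckets", so inpatient cost is modelled on its own. The model is to contain "factors for study arm and health care system/clinic strata", and "Results will be stratified by healthcare system".

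The revised SAP is looser. Section 3.2 offers generalized gamma regression as an example of an appropriate model for cost and mentions standardisation as a way to report on interpretable scales. Section 1 keeps cost components in scope ("with cost and utilization also assessed for specific components as described below") and sets the time point ("These outcomes will also be assessed at 12 months"). Section 2 also allows longer follow-up of secondary outcomes, "up to 3 years depending on when they are enrolled during years 2-3".

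Both documents build inpatient cost from payment weights applied to DRGs, and both require analysis of all randomised patients. Neither mentions zero costs, a two-part model, an added constant or a restriction to users of care. SAP section 2 refers twice to a separate health economics plan for further detail.

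**The concern.** If inpatient cost is a sum of DRG payments, a patient with no admission in the window has no DRG and a cost of exactly zero. That step is an inference from the costing method, but it is the natural reading. Most patients in the trial will not be admitted within a year. Generalized gamma, gamma, lognormal and Weibull distributions are continuous on positive values and give no probability to zero.

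The named model and the stated analysis population therefore do not fit together for this variable. An analyst holding only the protocol and SAP would have to choose a remedy after seeing the data. One possible choice, fitting positive costs only, would compare arms among patients selected by an event after randomisation. It would depart from the all-randomised rule and leave any effect on the chance of admission out of the cost estimate.

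**Working it through.** **Inputs.** One-year all-cause hospitalisation from the SAP 3.2 table: Denver Health 792/9149, VA 332/2447. No rate is given for UCHealth. Enrolment from the SAP (Achieved sample sizes 3/2023): 7,266 at Denver Health, 1,235 at the VA, 1,000 at UCHealth, total 9,501. With equal allocation to four arms, 9,501/4 = about 2,375 per arm.

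**1. Reproduce the printed rates.** 792/9149 = 8.66%, printed 8.7%. 332/2447 = 13.57%, printed 13.6%. Both agree.

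**2. Share with no admission (1 − x/n).**
- Denver Health: 8,357/9,149 = 91.3%.
- VA: 2,115/2,447 = 86.4%.
- Both together: 10,472/11,596 = 90.3%.

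**3. Project to the trial.** Expected patients with a positive inpatient cost, per arm:
- Denver Health: 7,266 × 0.0866 / 4 = about 157.
- VA: 1,235 × 0.1357 / 4 = about 42.
- UCHealth: 1,000 × u / 4, where u is its unknown rate. If u lies between the other two rates (assumption), this is about 22 to 34.
- Sum: about 221 to 233 of 2,375, that is 90.7% to 90.2% zeros. With u at 5% or 30% (assumption only), zeros are 91.1% or 88.5%. The missing rate does not affect the conclusion.

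**4. Likelihood at zero.** Near zero the generalized gamma density behaves like y^(c−1), where c is the product of its shape parameters (the ordinary shape parameter for gamma and Weibull). Its log at y = 0 is minus infinity for c > 1, plus infinity for c < 1, and finite only at c = 1 exactly. With zeros in the data, any c < 1 makes the total likelihood infinite, so no maximum-likelihood estimate exists. The lognormal log-density at zero is minus infinity for every parameter value. Numerical evaluation gave minus infinity for lognormal, gamma with shape 2, Weibull with shape 1.5 and a generalized gamma case, and plus infinity for gamma with shape 0.5.

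**5. Estimating equations.** With a log link, gamma working variance and arm as the only term, the equation for arm a is Σ(y − μ_a)/μ_a = 0. Its solution is the arm mean with zeros included, so the obstacle in step 4 is specific to full likelihood.

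**6. Longer follow-up.** If a full 3 years were used, and yearly risk were constant and independent (assumption), zeros would be 0.9134³ = 76% at Denver Health and 0.8643³ = 65% at the VA. They would still be the majority.

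**The case against.** *The revised SAP does not commit to this model.* It words generalized gamma as an example among appropriate models. This stands as far as it goes: the firm specification is in the protocol. A reader might infer that the protocol's cost paragraph is carried over unchanged, because the SAP's summary of revision says "The changes of substance occur only in Sections 3.1.a-e". The documents do not support that. The sentence refers to an original SAP, and the protocol text is not shown to be that document. Outside those sections the two already differ: 8 against 17 clinics, medication strata of 1-4 against 1-2 or 3+, and SD 0.247 with N=154 per arm against SD 0.22 with N=119. What remains is that the SAP repeats the model for cost and names no other.

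*The health economics plan may settle it.* This also stands. Handling of zero costs is the sort of detail such a plan would hold. Only the absence of a rule or cross-reference in the protocol and SAP can be shown.

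*Gamma models can accept zeros.* Correct for a log-link mean model with robust variance (step 5), so a reader should not infer that no gamma-type analysis is possible. The documents do not say this route is meant.

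*The harm is hypothetical.* Fair. Nothing in the documents plans to drop zeros, the all-randomised rule points the other way, and hospitalisation is analysed in its own right.

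*The table may be unreliable.* In the same table the all-cause ED percentages do not match their counts (1700/9149 = 18.6%, printed 1.9%; 1093/2447 = 44.7%, printed 4.5%). That is a separate item. The hospitalisation row is consistent, and only that row is used here.

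**Conclusion.** The point holds at minor severity. For inpatient cost, the model named in the protocol and repeated as the SAP's example cannot be fitted by maximum likelihood to all randomised patients, because about 91% at Denver Health and 86% at the VA are projected to have exact zeros.

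This rests on three assumptions: that no admission means zero inpatient cost, that the 2017-2018 cohort resembles the trial's patients, and that the window is 12 months. None is critical, since any material share of zeros leads to the same conclusion.

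A reader might infer that the cost analysis as a whole fails, or that the inpatient result will be biased. Neither follows. The documents give no zero share for total, outpatient or pharmacy cost, no arm difference in admissions and no cost per admission, so no size or direction of bias can be stated.

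**What to change.** For inpatient cost, and for any other component with a material share of zeros, replace the single generalized gamma model in SAP 3.2 with one that keeps the zeros:

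- Part 1: logistic regression for any cost. Part 2: generalized gamma regression for positive cost. Both include arm, with health care system as a factor.
- For each randomised patient and each arm, multiply the predicted probability of any cost by the predicted mean positive cost. Average over all patients and take differences between arms. This is the standardisation already planned (protocol, Treatment comparisons; SAP 3.2). Take intervals from the bootstrap.
- Report the zero share by component and arm.

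A log-link mean model with robust variance, fitted to all patients, is an acceptable equivalent. If the health economics plan already has a rule for zeros, a cross-reference in the SAP is enough.

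The cost is a paragraph of SAP text and one extra regression per affected component, with bootstrap runs. The fix does not rescue the by-system results: with about 42 positive inpatient costs per arm at the VA and about 22 to 34 at UCHealth, those estimates are likely to be unstable and should be labelled so.

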- a) If a patient texts "stop" to unsubscribe, the patient is automatically withdrawn from receiving the intervention (messages). Patients may also text misspellings of the word "stop" (such as "tsop," etc.), or send a message indicating the patient would like to be removed from the study. We will continue to view already-collected, standard of care data from these patients.
 - In the initial version of the consent form, we described a "stop" response as a way to "fully withdraw" from the study. These patients were opted out from the study entirely, and data are no longer being collected on these patients. In v.12.3.19 of the info sheet, the language was amended. For patients that have hit "stop" in the original cohort, researchers will call the patients (please find script) to obtain verbal consent to collect their data moving forward. If patients do not consent or cannot be reached after two attempts, we will continue to treat the patients as fully opted out and we will not view their data moving forward. Patients from this original cohort that hit "stop" in the future will be flagged and the calling process will be implemented.
- b) Should a patient respond "done" to indicate they have already filled their prescription or a physician has cancelled their medication, we will stop sending patients any further text messages about refilling the medication in which they had a delay until their medication is again due for a refill (i.e. 30 – 90 days in the future). We will immediately remove the patient from further text messages for this instance of medication nonadherence.
 - Misspellings of "done" or messages indicating they have already filled their prescription or that a physician cancelled their medications will be treated as if they responded "done." If a physician has stopped their medication, we will no longer monitor for medication refills for that specific medication. For other medications, we will resume following the other medication refills. If the patient has a refill gap for the same or for other medications again, we will start delivering text messages within the same arm that they had been previously randomized to.
- c) Patients may request Spanish messages at any time via text. We will start to deliver Spanish language texts following the request. If the patient meets additional criteria for texts during the duration of the study, they will receive Spanish language texts.

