In addition, we will update the patient's care provider on a regular basis about medication gaps and other medication issues of their patients. The frequency and mode of contact will be based on their indicated preference, which we will solicit at the start of the study during our clinic presentation. If the provider did not indicate a preference, we will send this information via email on a weekly basis.

Quantitative Analysis

The study will be a randomized controlled study with four treatment arms. When patients are identified through pharmacy refill data to have a 7-day gap in any prescribed CV medication refills, they will be randomized to one of four arms, described in Intervention below. Randomization will be stratified within each of the eight clinics, and within strata defined by number of other CV medication classes that are prescribed at randomization (1-4), using blocks of 4 patients to ensure balance within clinics over time. Thus, within each clinic and number of other medication stratum, each set of 4 consecutively enrolled subjects will be randomized to the four study arms. Treatments will be initiated immediately upon randomization, in response to the 7-day gap.

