Available sample sizes: We obtained data from each of the three health care systems on the number of patients at the eight specific clinics (VA, 2 clinics; UCHealth, 4 clinics; DH, 2 clinics) to be included in this study. Figure 1 below shows estimated numbers of patients seen, numbers with CVD conditions and prescribed CVD medications, and numbers with 7 day gap. These patients will be invited to participate, and assuming 80% agree to participate, and 90% of those yield usable outcome data, we expect to have usable outcome data for about 4,364 patients, or about 1,091 per treatment arm. Thus, we expect to have ample subjects (about seven times as many as needed) to achieve the necessary power for the primary analysis of PDC. Additional subjects will provide power for secondary analyses, and for analyses of secondary outcomes.

Exploratory

Covid Messaging

On April 6, 2020, the Nudge Study started to send Covid messages to patients enrolled in the study (Amendment PAM006-1, approved March 18, 2020).

This study plans to scale the concept of the Nudge Study to other applications in the future. We propose pulling data regarding Covid testing of patients sent messages after April 6, 2020 to compare with Arm 1 (non interventional arm).

Comparing opt out vs opt in demographics

There is a growing interest in learning more about who is opting out of our study, as well as who is opting in.

Our study plans to compare the demographics of patients (race, age, ethnicity, gender) that have opted in vs opted out of our study. This requires pulling data from Electronic Health records to compare both cohorts.

We propose (12/1/20) to retrospectively pull demographic data from the EHR for patients that have opted out of the study (race, age, ethnicity, gender) to compare these data with patients that have opted in to the Nudge study. Moving forward, we will include a statement in the opt out packet (**Information Sheet**, v 12/1/20) to inform potentially-eligible patients that receive an opt out packet that demographic information will be drawn.

Qualitative Analysis

Assessment of patient perspectives

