Study description: This individually randomized three-center trial will compare three behavioral nudges based on text and chatbot messaging with usual care to improve adherence to cardiovascular medications.

Setting: The study will be conducted in 17 primary care clinics within 3 health care systems (University of Colorado Health, VA Eastern Colorado Health Care System, and Denver Health Medical Center).

Design: The study will be an individually randomized controlled study with four treatment arms (details of interventions below). Patients become eligible for the study when identified through pharmacy refill data to have a 7-day gap in any prescribed CV medication refills. Eligible patients will be randomized to one of four arms. Randomization will be stratified within each of the clinics, and further stratified within clinics by patients with 1-2 vs 3 or more active CV medication classes at baseline, and using blocks of 4 patients to ensure balance within clinics over time. Thus, within each clinic and number of other medication stratum, each set of 4 consecutively enrolled subjects will be randomized to the four study arms. Treatments will be initiated immediately upon randomization, in response to the 7-day gap.

Intervention: The four treatment arms will be 1) usual care (control); 2) generic text message reminder; 3) text message behavioral nudges only; or 4) text message behavioral nudge plus a pre-programmed AI interactive chat bot designed to identify and resolve barriers to medication refill and adherence.

Delivery of treatments will be as follows:

For patients randomized to one of the three active intervention arms:

- If a patient gaps on a medication at baseline, they receive a text to refill that medication.
 - If a patient gaps on multiple medications at baseline, they receive only one text about all of the medications they gapped on.

- If a patient later gaps on any study medication, they will receive a reminder, regardless of whether they had gapped on or been prescribed the medication at baseline.
- If a patient is removed from a medication, no further texts are sent for that medication. Patients randomized to the control arm receive no texts or other reminders.

2. Study outcomes

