Several sources of cost data will be used. To capture costs of development, implementation and maintenance of the intervention, we will develop instruments (e.g. time logs) and procedures to prospectively capture resource use associated with the intervention including what was done, who did it, how long it took, and what nonhuman resources were required. This is further discussed in greater detail in the health economics plan. In brief, intervention costs will be the cost of implementing the intervention excluding research and development costs. Costs associated with healthcare utilization will also be estimated using a resource-based method previously developed to assign costs to encounter data. Inpatient utilization will be measured using diagnostic-related groups (DRGs), outpatient utilization using relative value units (RVUs), and cost of pharmacy utilization using the midpoint between the Federal Supply Schedule (FSS) and the National Average Drug Acquisition Cost (NADAC). Inpatient costs will be estimated by applying national payment weights to DRGs, outpatient costs by applying a national conversion factor to RVUs, and pharmacy costs as the median between the FSS and NADAC. Please refer to health economic plan analysis for further details.

3. Statistical analysis plan

Analyses will be based on the intent to treat principle, using all patients who were randomized.

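### The exploratory Covid-testing comparison sets patients who were sent messages against all of Arm 1, so it can carry selection bias that a comparison by randomized arm would largely avoid.

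*Combined protocol and SAP*

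**What the plan says.** The Covid Messaging item (protocol, Exploratory) reports that from April 6, 2020 the study "started to send Covid messages to patients enrolled in the study". It then proposes to obtain Covid-testing data on "patients sent messages after April 6, 2020 to compare with Arm 1 (non interventional arm". It does not say who was eligible for a Covid message, what triggered one, whether all of Arms 2-4 were covered, when the testing window opens in Arm 1, or how the comparison will be analysed.

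Four other places bear on it:

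- **Plan for responding to text messages from patients, item a:** after a STOP, "the patient is automatically withdrawn from receiving the intervention (messages". The same item describes an original cohort, recruited before the information sheet was amended (v.12.3.19), in which STOP meant full withdrawal. Data on those patients are not viewed further unless they consent again by telephone.
- **SAP section 1, delivery of treatments:** "Patients randomized to the control arm receive no texts or other reminders".
- **Protocol, Quantitative Analysis:** "each set of 4 consecutively enrolled subjects will be randomized to the four study arms", so allocation is 1:1:1:1.
- **Protocol, Planned Analysis, and SAP section 3:** "Analyses will be based on the intent to treat principle, using all patients who were randomized". The Covid item does not refer to this rule.

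**The concern.** STOP can occur only in the texted arms. A patient in Arms 2-4 who stopped before the first Covid message is not among those sent one. The corresponding Arm 1 patient, who would have stopped if texted, cannot be identified and remains in the comparator. If people who stop messages differ from the rest in how readily they are tested for Covid, the two groups differ at the outset for reasons unrelated to the messages.

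Arm 1 also has no message date, so the time over which testing is counted has no natural start there. Unless one rule is set for all arms, the groups could differ in calendar time as well.

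What is at stake is limited to the Covid-testing result. The protocol mentions it next to its plan to extend the Nudge concept to other applications, so a misleading result could carry into later work.

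**Working it through.** **Was the messaged group probably smaller than Arms 2-4?** The STOP rule speaks of original-cohort patients who had already stopped under wording replaced in v.12.3.19, which is before April 2020. SAP 3.1.a (missing and truncated follow-up) agrees: a small percentage of early patients have shortened observation because they opted out. Some STOPs therefore very probably came before the first Covid message, and messaging those patients would have contradicted the STOP rule. Anyone who stopped after a Covid message still counts as sent.

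Two other routes out of the messaged group are possible but not established:

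- Landline-only patients meet the entry criteria, yet the Mobile Messenger section has a listed cell phone confirmed first. It is not stated whether Arm 1 is checked in the same way.
- Under SAP section 1, "If a patient later gaps on any study medication, they will receive a reminder". If Covid messages followed refill texts, being sent one would depend on a new gap. The documents do not say.

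**Size.** The plan gives no rate, effect size or sample size for this analysis, so there is no figure to reproduce. Let f be the share of Arms 2-4 sent a message, and p_sent and p_unsent the testing rates in the two kinds of patient, with no message effect. By randomization Arm 1 has the same mix:

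- Arm 1 rate = f × p_sent + (1 − f) × p_unsent
- Bias = p_sent − Arm 1 rate = (1 − f) × (p_sent − p_unsent)

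Assumed inputs: 5% to 15% not sent; testing 30% in those sent and 15% to 20% in those not sent. SAP 3.1.f uses 15% for opt-out after randomization, but that planning figure is not specific to STOP before a Covid message.

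- Low end: 0.05 × (30 − 20) = 0.5 points; Arm 1 rate 29.5%.
- High end: 0.15 × (30 − 15) = 2.25 points; Arm 1 rate 27.75%.
- f = 1: 0 points.

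**False-positive rate of the written contrast.** Two-sided 0.05 normal test, 3 × f × n messaged patients against n in Arm 1. The number per arm for the Covid comparison is not given. I used n = 5,000/4 = 1,250 (planned enrollment) and n = (1,235 + 7,266 + 1,000)/4 ≈ 2,375 (achieved), both from SAP 3.1.f.

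| Case | n per arm | Bias (points) | SE (points) | False-positive rate |
|---|---|---|---|---|
| Low | 1,250 | 0.5 | 1.50 | about 6% |
| Low | 2,375 | 0.5 | 1.09 | about 7% |
| High | 1,250 | 2.25 | 1.50 | about 32% |
| High | 2,375 | 2.25 | 1.09 | about 54% |

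For example, high end with n = 1,250: SE = √(0.30 × 0.70/3,187.5 + 0.2775 × 0.7225/1,250) = 0.0150, and 0.0225/0.0150 = 1.5 standard errors.

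**As-randomized alternative.** With complete data its selection bias is 0 at every f, and its false-positive rate is 5%. Its cost is dilution. Assuming 20% testing in Arm 1 and a gain of 5 points in those messaged, the expected difference is 5 × f points and power is:

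| Share messaged | n = 1,250 | n = 2,375 |
|---|---|---|
| 100% | 95.6% | 99.9% |
| 95% | 93.6% | 99.8% |
| 90% | 91.1% | 99.6% |
| 75% | 78.9% | 96.9% |
| 50% | 45.6% | 72.8% |

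**The case against.** The strongest reply is that the sentence may be shorthand. Control patients get no texts, so patients sent messages could simply mean Arms 2-4. If every patient in those arms was sent a Covid message, the two contrasts are the same and nothing is lost. The amendment that set up the messages is cited but is not part of these documents, so this cannot be ruled out. It would, however, require messaging patients already withdrawn from messages. As a literal description of the data pull, the sentence still leaves unmessaged patients out.

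Several stronger readings are tempting, and the documents do not support them:

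- **That randomization is certainly lost.** This depends on f being below 1, which is probable but not shown.
- **That the messaged-only contrast has no benefit.** It avoids dilution and addresses a different question. The fair statement is that the plan gives no reason for choosing it.
- **That patients who could not be texted are excluded.** The phone provisions leave this open.
- **That the intent-to-treat rule is breached.** The rule is stated for the planned analyses, and the Covid item is a brief exploratory proposal with no model or test. It is better described as not saying whether the rule applies.

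Two further points stand. The testing rates, and even the direction of the gap, are assumptions. And an as-randomized comparison is not fully recoverable: original-cohort STOP patients who did not consent again are missing from Arms 2-4 only. If all unmessaged patients were of that kind, the two contrasts would coincide again.

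**Conclusion.** The point holds as a possible selection bias in how an exploratory comparison is written. Its size cannot be known from the documents. It is 0 if all of Arms 2-4 were sent a Covid message, and about 0.5 to 2.25 percentage points if 5% to 15% were not and their testing rate was 10 to 15 points lower. The low end hardly matters; the high end could produce a false finding about a third to a half of the time at the trial's planned and achieved sizes. All of this rests on assumed shares and rates. A reader might infer that the Covid result is shown to be biased, or that the trial's main findings are affected. Neither follows: the bias is possible rather than demonstrated, and no primary or secondary outcome uses this comparison. I would label it a cheap improvement.

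**What to change.** Rewrite the Covid item so that:

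1. The main comparison is all patients randomized to Arms 2-4, pooled and by arm, against all patients randomized to Arm 1, whether or not a message was sent.
2. The testing window starts in every arm at the later of April 6, 2020 and randomization, with a common end rule. A start at April 6 for everyone would count testing before randomization in patients who joined later.
3. The report gives, by arm, the share sent a Covid message and the number whose data cannot be used after an original-cohort STOP.
4. The messaged-only contrast is kept as supportive.

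The cost is a few sentences and a slightly larger record pull, to include unmessaged patients in Arms 2-4 whose data may still be used. The statistical price is dilution: small if nearly all were messaged, appreciable if only half were. The reported share messaged will show which applies. Missing original-cohort STOP patients remain a limitation to state.
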